#### 1.1.2. Estimands

The primary clinical question of interest is: What is the intervention difference between tirzepatide 10 mg and/or 15 mg QW and placebo, when used in conjunction with a reduced-calorie diet and increased physical activity for weight management, in mean percent change in body weight, and proportion of participants who achieve  $\geq$ 5% body weight reduction, from randomization to 72 weeks, in obesity disease participants with BMI  $\geq$ 27 kg/m² and at least 2 obesity-related health problems, or participants with BMI  $\geq$ 35 kg/m² and at least 1 obesity-related health problem? The obesity-related health problems are defined as IGT, hyperlipidemia, and NAFLD.

#### 1.1.2.1. Primary estimand

The estimand is described by the following attributes:

- Population: all randomized participants who received at least 1 dose of treatment.
- Endpoint: mean percent change from randomization to Week 72 in body weight, AND percentage of study participants who achieve ≥5% body weight reduction from randomization to Week 72.
- Treatment condition of interest: tirzepatide 10 mg and/or 15 mg QW vs. placebo, excluding data after discontinuation of study drug. Temporary interruptions and modification prior to discontinuation will be allowed as part of the treatment conditions.
- Handling of intercurrent events: the intercurrent events of treatment discontinuation for any reason is addressed by the treatment condition of interest attribute and handled by the hypothetical strategy.
- Population-level summary: difference in mean percent changes between treatment conditions, AND difference in response percentage between treatment conditions.

Rationale for estimand: the estimand aims to reflect treatment efficacy in an envisaged scenario in which the intercurrent events leading to treatment discontinuation would not occur.

This estimand is referred to as 'efficacy' estimand in the latter of this document.

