Study GPHZ is a Phase 3, multicenter, randomized, placebo-controlled, double-blinded study to evaluate the safety and efficacy of tirzepatide 10 mg and 15 mg administered subcutaneously once weekly compared with placebo when used in conjunction with a reduced-calorie diet and increased physical activity for weight management, in participants who have

- \cdot A BMI of 27 kg/m² or greater and less than 35 kg/m² and at least 2 obesity-related health problems; OR
- · A BMI of 35 kg/m² or greater and at least 1 obesity-related health problem.

Obesity-related health problems are defined as IGT, hyperlipidemia, or NAFLD.

All participants will undergo a 4-week screening period and a 72-week treatment period including a 20-week dose escalation. The safety follow-up period will be 4 weeks.

Study participants will be randomized in a 1:1:1 ratio to tirzepatide 10 mg QW, tirzepatide 15 mg QW, or placebo QW, stratified by

- baseline IGT (yes or no)
- baseline hyperlipidemia (yes or no)
- baseline NAFLD (yes or no), and
- sex (male, female).

Disclosure Statement:

This is a parallel group-treatment study with 3 arms that is participant- and investigator-blinded.

[figure not shown]
Number of Participants:

Approximately 348 participants will be screened to achieve 261 randomly assigned to study intervention for an estimated total of 87 evaluable participants per intervention group.

Intervention Groups and Duration:

All doses will be subcutaneously administered once-weekly using single-use pens. The starting dose of tirzepatide will be 2.5 mg QW (or matching placebo) for 4 weeks, then the dose will be increased by 2.5 mg (or matching placebo) every 4 weeks: 2.5 to 5 to 7.5 to 10 mg for those randomized to 10 mg, and continuing to 12.5 to 15 mg for those randomized to 15 mg.

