6.7.1. Management of Participants with Gastrointestinal Symptoms

Participants who experience intolerable GI symptoms (for example; nausea, vomiting, or diarrhea) at any time during the study, should first be counselled on dietary behaviors that may help mitigate nausea and vomiting, (for example, eating smaller meals, splitting 3 daily meals into 4 or more smaller ones, and stopping eating when they feel full). If symptoms persist, the participant should be prescribed, at the investigator's discretion, symptomatic medication (for example, antiemetic or antidiarrheal medication).

Temporary interruption

A temporary interruption of study intervention for 1 dose is permitted, provided the participant has taken the last 3 weekly doses. Study treatment should be resumed immediately, either alone or in combination with symptomatic medication, which can also be utilized to manage symptoms. Management of study intervention after interruptions >1 dose is discussed in Section 7.

Dose modification

If intolerable GI symptoms (for example, nausea, vomiting, or diarrhea) persist despite the above measures, the investigator should contact Lilly to consider reinitiating study intervention at the next lowest maintenance dose in a blinded fashion (for example, 15 mg and 12.5 mg reduced to 10 mg, 10 mg or lower reduced to placebo). Only 1 dose reduction per participant will be permitted during the course of the study. The dose modification is not allowed without prior discussion with Lilly's CRP and/or CRS.

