7.1.1. Temporary Study Drug Discontinuation

In certain situations, after randomization, the investigator may need to temporarily interrupt study drug. Every effort should be made by the investigator to maintain participants on study drug and to restart study drug after any temporary interruption, as soon as it is safe to do so. Distribution of study medication at the correct dose will be per IWRS instructions.

If study drug interruption is	then
2 consecutive doses or less	participant restarts study drug at last administered dose, as per escalation schedule.
3 consecutive doses or more	participant restarts study drug (at 5 mg, managed by IWRS) and repeats dose escalation scheme.
due to an AE	the event is to be documented and followed according to the procedures in Section 8.3 of this protocol.
due to intolerable persistent GI AE	participants should be treated as suggested in Section 10.8.

Abbreviations: AE = adverse event; GI = gastrointestinal; IWRS = interactive web response service.

Investigators should inform Lilly that study drug has been temporarily interrupted. The data related to temporary interruption of study treatment will be documented in source documents and entered on the eCRF.

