# 3. Analysis Sets

For purposes of analysis, the following populations are defined:

Table GPHZ.3.1. Description of Analysis Populations

Population	Description
Entered	All participants who sign informed consent form (ICF)
Randomized	All participants who are randomly assigned a study drug.
Modified Intent-to-Treat (mITT)	All randomly assigned participants who are exposed to at least 1 dose of study drug. Participants will be included in the treatment group to which they were randomized.

Table GPHZ.3.2. Description of Analysis Datasets

Analysis Datasets	Description
Efficacy Analysis Set (EAS)	Data obtained during the treatment period from the modified intent-to-treat (mITT) population, excluding data after discontinuation of study drug (last dose date + 7 days)
	Regarding imaging measurements (MRI and CT), data obtained during the treatment period from the mITT population, excluding data after discontinuation of study drug (last dose date + 14 days)
Full Analysis Set (FAS)	Data obtained during treatment period from the mITT population, regardless of adherence to study drug.
Safety Analysis Set (SS)	Data obtained during the treatment plus follow up period from the mITT population, regardless of adherence to study drug.

Unless otherwise specified, for analyses guided by the "efficacy" estimand, EAS will be used. For analyses guided by the "treatment-regimen" estimand, FAS will be used. For safety analysis, SS will be used.

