#### 4.3.3. Supplementary analyses

#### 4.3.3.1. Analysis Related to the Treatment Regimen Estimand

The analysis related to the "treatment-regimen" estimand will be conducted using data in the FAS.

The analysis for the mean percent change in body weight will be conducted utilizing ANCOVA. The response variable for the ANCOVA model will be percent change in body weight from randomization to Week 72. This model will include terms of baseline IGT (yes or no); baseline hyperlipidemia (based on TG; yes or no); baseline NAFLD (yes or no) and sex (female, male) as fixed effects and baseline body weight as a covariate. The ANCOVA analysis will be conducted with multiple imputation of missing body weight at Week 72 and statistical inference over multiple imputation of missing data guided by Rubin (1987).

With the aid of the ANCOVA model, 2-sided 95% CI for mean change in percent body weight from baseline to the 72-week visit between tirzepatide 10 mg or 15 mg QW and placebo will be derived.

With the aid of the logistic regression model, 2-sided 95% CI and odds ratio for percentage of participants achieving at least 5% body weight reduction from baseline to the 72-week visit between tirzepatide 10 mg or 15 mg QW and placebo will be derived.

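### Do weights taken after a blinded move to placebo for gastrointestinal intolerance undermine the primary tirzepatide estimate?

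*SAP*

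**What the plan says.** Protocol 6.6 permits a dose change only to manage intolerable gastrointestinal symptoms and refers to 6.7.1. There, under a heading on dose modification, the step-down is illustrated as "for example, 15 mg and 12.5 mg reduced to 10 mg, 10 mg or lower reduced to placebo". It is blinded, follows dietary advice, symptomatic medication and interruption, and requires prior discussion with the sponsor. Also, "Only 1 dose reduction per participant will be permitted during the course of the study". Protocol 7.1 places permanent discontinuation after this step. Protocol 6 counts placebo as study intervention.

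In the SAP, the primary estimand (1.1.2.1) says "Temporary interruptions and modification prior to discontinuation will be allowed as part of the treatment conditions". It names only treatment discontinuation as an intercurrent event and gives it the hypothetical strategy. Table GPHZ.3.2 defines the EAS as treatment-period data "excluding data after discontinuation of study drug (last dose date + 7 days"). The supplementary treatment-regimen "estimand will be conducted using data in the FAS", which holds "Data obtained during treatment period from the mITT population, regardless of adherence to study drug". SAP 6.2 summarises dose de-escalation if the data warrant it. It has no placebo category.

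**The concern.** Consider two participants randomised to 10 mg who stop tolerating the drug in the same week. One stops injecting: later weights leave the EAS and are handled as missing at random. The other is moved to placebo and keeps injecting: later weights stay in the EAS as tirzepatide 10 mg data. Their active-drug exposure is the same but their contribution to the primary estimate differs, and the SAP never says that this is intended. It sits awkwardly with a hypothetical estimand whose treatment condition is tirzepatide 10 mg or 15 mg once weekly.

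The supplementary analysis does not help, because the Full Analysis Set (FAS) also keeps these weights. The retrieved-dropout pool in SAP 4.3.3.2 depends on the same classification. With no separate count, a reader of the report could not tell how many participants were involved. What is at stake is the meaning of the estimates for both co-primary endpoints and for the secondary endpoints that use the EAS.

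**Working it through.** **How the text classes the move.**

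1. Protocol 6.6 allows one kind of dose modification, and Protocol 6.7.1 lists the step to placebo under it.
2. Study drug in the SAP must include placebo, since the placebo arm enters the modified intent-to-treat population through a dose of study drug. The EAS cut-off therefore runs from the last injection, whether active or placebo.
3. SAP 1.1.2.1 keeps modification within the treatment condition. The only dose modification the protocol allows is the one in 6.7.1.
4. The retrieved-dropout pool requires early discontinuation of study drug. A participant still injecting after a modification has not discontinued, so is not in the pool.

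The move is classed by implication, though not named.

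**Who can be affected.** In the 10 mg arm, a move to placebo is possible throughout. In the 15 mg arm it is possible only while the participant is at 10 mg or lower, since titration runs through 10 mg before "and continuing to 12.5 to 15 mg for those randomized to 15 mg". That is 4 steps (2.5, 5, 7.5, 10 mg) × 4 weeks = 16 weeks in the initial escalation. After an interruption of 3 or more doses the "participant restarts study drug (at 5 mg, managed by IWRS) and repeats dose escalation scheme", which adds 3 steps (5, 7.5, 10 mg) × 4 weeks = 12 weeks. A 15 mg participant already reduced to 10 mg has used the single permitted reduction.

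**Planned power.** Inputs from SAP 5: difference 11 points, SD 10, 87 per arm, 25% dropout, two-sided alpha 0.025, responders 25% against 90%. Observed per arm: 87 × 0.75 = 65.25, taken as 65. SE = 10 × √(2/65) = 1.754. Power for the two-sample t-test (noncentral t) is 0.99996, and for Fisher's exact test above 0.9999. The stated figure of more than 90% is reproduced with much to spare.

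**Dilution.** Let f be the share of a tirzepatide arm's observed Week 72 data that comes from participants moved to placebo. The documents do not give f, so it is assumed. Assume also that those moved keep none of the effect.

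- Weight difference: 11(1 − f), a loss of 11f.
- Responder rate: 90 − 65f percentage points.
- Tirzepatide-arm variance: 100 + 121f(1 − f); placebo variance 100.

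| f | Weight difference | Loss | Loss / SE (n = 65) | Responders | t-test power (n = 65) |
|---|---|---|---|---|---|
| 2% | 10.78 | 0.22 | 0.13 | 88.7% | 0.9999 |
| 5% | 10.45 | 0.55 | 0.31 | 86.75% | 0.9998 |
| 10% | 9.90 | 1.10 | 0.63 | 83.5% | 0.9993 |
| 20% | 8.80 | 2.20 | 1.25 | 77.0% | 0.994 |
| 30% | 7.70 | 3.30 | 1.88 | 70.5% | 0.968 |

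Responder power (normal approximation, n = 65) is at least 0.9995 up to f = 30%. The t-test falls through 90% between f = 39% (0.903) and f = 40% (0.893).

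The table assumes that moved and unmoved participants drop out equally. If all those moved stay to Week 72 while 25% of the arm drops out, a randomised share p becomes f = p/0.75. Then p = 2%, 5% and 10% cost 0.29, 0.73 and 1.47 weight points, and the 39% limit corresponds to p = 0.39 × 0.75 = 29%. With no dropout at all (n = 87) the SE is 10 × √(2/87) = 1.516, the ratios at 2%, 5% and 10% are 0.15, 0.36 and 0.73, and power holds above 90% to about f = 47%. If half the effect is retained, each weight loss halves.

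**The case for a change.** The best argument for acting is that an estimand should say outright which states are modifications and which are intercurrent events. Loss of all active drug is an odd thing to leave to inference. Clarifying it would take a sentence or two in the SAP, one dispensing-system date and a row in a table. The optional dose-by-visit display covers only the escalation period, and compliance counts injections whatever their strength, so the move could go unreported.

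The observation about reporting stands: there is no firm commitment to a count and no placebo category. The proposed sentence, however, would restate what the documents already imply.

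An added analysis is harder to defend. Cutting the tirzepatide arms at the last active dose leaves placebo participants uncut after the same blinded step, and leans on missing at random for gastrointestinal-intolerant participants in the active arms only. Cutting every arm at the step also discards weights after a reduction from 15 mg to 10 mg, which the estimand deliberately keeps. Neither isolates the effect of moving to placebo, and statisticians could reasonably disagree about running either.

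**Conclusion.** No change follows. The plan leaves the case unnamed, but its wording leads to a single working rule: the move is a modification, the weights stay in the EAS under the randomised arm, and the participant is not a retrieved dropout. Keeping the weights is a fair trade-off. It treats the arms alike after a blinded step, and it dilutes the tirzepatide effect. Under complete loss of effect the dilution is 0.11 weight points and 0.65 responder points for each 1% of observed Week 72 data that comes from participants moved. Superiority is not threatened unless roughly 29% to 39% of an arm is moved, on the basis of 65 observed per arm.

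This rests on an assumed share moved, since the documents give none, and on the planning values in SAP 5. The flow chart in Protocol Appendix 8 is not reproduced in the text reviewed; if it classes the step differently, analysts would need to reconcile it with SAP 1.1.2.1. A separate count of moves to placebo in the report would be a courtesy to readers and can be given within the de-escalation summary of SAP 6.2.

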#### **1.1.2.2.** Supplemental estimand(s)

The estimand is described by the following attributes:

- Population: all randomized participants who received at least 1 dose of treatment.
- Endpoint: mean percent change, from randomization to Week 72, in body weight, AND percentage of study participants who achieve ≥5% body weight reduction from randomization to Week 72.
- Treatment condition of interest: tirzepatide 10 mg and/or 15 mg vs. placebo, **regardless** of study drug adherence.
- Handling of intercurrent events: the intercurrent events of treatment discontinuation for any reason is addressed by the treatment condition of interest attribute, and handled by treatment policy strategy. Further details can be found in Section 4.3.3.1.
- Population-level summary: difference in mean percent changes between treatment conditions, AND difference in response percentage between treatment conditions.

Rationale for estimand: This aims at reflecting how participants with obesity disease with obesity-related health problems, are treated in clinical practice, and take into account both safety and efficacy.

This *de facto estimand* is referred to as the 'treatment-regimen' estimand in the latter sections of this document.

## 1.2. Study Design

Study GPHZ is a Phase 3, multicenter, randomized, placebo-controlled, double-blinded study to evaluate the safety and efficacy of tirzepatide 10 mg and 15 mg administered subcutaneously once weekly compared with placebo when used in conjunction with a reduced-calorie diet and increased physical activity for weight management, in participants who have

[figure not shown]
- · A BMI of 27 kg/m² or greater and less than 35 kg/m² and at least 2 obesity-related health problems; OR
- A BMI of 35 kg/m^2 or greater and at least 1 obesity-related health problem.

Obesity-related health problems are defined as IGT, hyperlipidemia, or NAFLD.

All participants will undergo a 4-week screening period and a 72-week treatment period including a 20-week dose escalation. The safety follow-up period will be 4 weeks.

Study participants will be randomized in a 1:1:1 ratio to tirzepatide 10 mg QW, tirzepatide 15 mg QW, or placebo QW, stratified by

- baseline IGT (yes or no)
- baseline hyperlipidemia (yes or no)
- baseline NAFLD (yes or no), and
- sex (male, female).

Abbreviations: QW= once weekly; T= telephone visit. All participants will be randomized to 72 weeks of treatment.

Figure 1.1. Study design for Clinical Protocol I8F-JE-GPHZ.

## 2. Statistical Hypotheses

The alternative hypotheses for the primary objective are the following:

- H10: QW tirzepatide 10 mg is superior to placebo for percent change in body weight from randomization AND percentage of participants who achieve ≥5% body weight reduction at 72 weeks.
- H15: QW tirzepatide 15 mg is superior to placebo for percent change in body weight from randomization AND percentage of participants who achieve ≥5% body weight reduction at 72 weeks.

The above 2 hypotheses will be tested in parallel, each at a 2-sided significance level of 0.025.

#### 2.1. Multiplicity Adjustment

The type 1 error will be controlled in the strong sense at a two-sided significance level of 0.05 because two hypotheses ( $H_{10}$  and  $H_{15}$ ) will be tested in parallel each at a 2-sided significance level of 0.025. Since superiority of each one of two hypotheses will be declared if and only if both statistical tests (regarding percent change in body weight and percentage of participants who achieve  $\geq$ 5% body weight reduction) are significant, no multiplicity adjustment is planned for these 2 tests.

# 3. Analysis Sets

For purposes of analysis, the following populations are defined:

Table GPHZ.3.1. Description of Analysis Populations

Population	Description
Entered	All participants who sign informed consent form (ICF)
Randomized	All participants who are randomly assigned a study drug.
Modified Intent-to-Treat (mITT)	All randomly assigned participants who are exposed to at least 1 dose of study drug. Participants will be included in the treatment group to which they were randomized.

Table GPHZ.3.2. Description of Analysis Datasets

Analysis Datasets	Description
Efficacy Analysis Set (EAS)	Data obtained during the treatment period from the modified intent-to-treat (mITT) population, excluding data after discontinuation of study drug (last dose date + 7 days)
	Regarding imaging measurements (MRI and CT), data obtained during the treatment period from the mITT population, excluding data after discontinuation of study drug (last dose date + 14 days)
Full Analysis Set (FAS)	Data obtained during treatment period from the mITT population, regardless of adherence to study drug.
Safety Analysis Set (SS)	Data obtained during the treatment plus follow up period from the mITT population, regardless of adherence to study drug.

Unless otherwise specified, for analyses guided by the "efficacy" estimand, EAS will be used. For analyses guided by the "treatment-regimen" estimand, FAS will be used. For safety analysis, SS will be used.

#### 4. Statistical Analyses

#### 4.1. General Considerations

Statistical analysis of this study will be the responsibility of Lilly or its designee. Any change to the data analysis methods described in the protocol will require an amendment ONLY if it changes a principal feature of the protocol. Any other change to the data analysis methods described in the protocol, and the justification for making the change, will be described in the SAP or the clinical study report. Additional exploratory data analyses may be conducted as deemed appropriate.

Unless otherwise noted, all tests of treatment effects will be conducted at a 2-sided alpha level of 0.05, and the confidence interval will be calculated at 95%, 2-sided. In statistical summaries and analyses, data will be analyzed as randomized.

Unless specified otherwise, efficacy and safety will be assessed using the modified intent-to-treat (mITT) population. Baseline is defined as the last non-missing data collected at randomization (prior to first dosing of study drug). Unless specified otherwise, safety assessments will be guided by an estimand comparing safety of tirzepatide doses with placebo irrespective of adherence to study drug. Thus, safety analysis will be conducted using SS.

Summary statistics for continuous measures will include sample size, mean, SD, median, minimum, and maximum. The analysis model to make comparisons among treatment groups relative to continuous measurements assessed over time will be a mixed model for repeated measures (MMRM), with terms of treatment, visit, and treatment by visit interaction, stratification factors, and baseline measurement as a covariate.

Kaplan Meier method will be used for estimation of cumulative event free survival rates over time, and Cox proportional hazards regression analysis will be used to compare hazard rates among treatments.

Summary statistics for categorical measures (including categorized continuous measures) will include sample size, frequency, and percentages. Logistic regression will be used to examine the treatment difference in binary efficacy outcomes if there is a need to adjust for covariates. Otherwise, Fisher's exact test will be used to examine the treatment difference in categorical outcomes.

Summary statistics for discrete count measures will include sample size, mean, SD, median, minimum, and maximum.

For the safety related parameters, the definition of baseline and postbaseline are specified in Table GPHZ.4.1.

Analysis Dataset	Analysis Type	Baseline	Postbaseline
SS	1.1) Treatment-Emergent Adverse Events	The baseline period is defined as the start of screening and ends prior to the first dose in of study treatment (typically at Week 0).	Starts after the first dose of study treatment and ends at the end of the study period (including off-drug follow up visit).
SS	1.2) Treatment-Emergent Abnormal Labs a , Vital Signs, and ECGs.	Baseline will include all scheduled and unscheduled measurements during the baseline period (Visit 1 to Visit 3)	Postbaseline will be defined as above (1.1). All scheduled and unscheduled measurements will be included.
SS	1.3) Change from Last Baseline to Week xx and to Last Postbaseline for Labs a ,Vital Signs, and ECGs.	The last scheduled and unscheduled non-missing assessment recorded during the baseline period defined above (1.2).	Postbaseline will be defined as above (1.1). Only scheduled visits will be included. The early discontinuation (ED) visits are considered scheduled visits.

Table GPHZ.4.1. Baseline and Postbaseline Definitions for Safety Analysis

Abbreviations: ECGs = electrocardiogram; SS = Safety Analysis Set.

For the primary and secondary efficacy endpoint analyses, data for participants with missing values at the 72-week visit will be imputed based on the method described in Section 4.3.2. Otherwise, missing values will not be explicitly imputed except for the parameters with only 1 postbaseline measure during the analysis period per schedule of activity, where last observation carried forward (LOCF) approach will be applied to impute the endpoint when ED measure is available.

End of study participation for a participant will be the earliest of date of death, date of withdrawal from further participation in the study, or date of safety follow-up visit (Visit 801). For participants considered to be lost-to-follow-up, end of study participation will be the date of lost-to-follow-up reported by the investigator. Participant data included in the database after the last date of study participation (including safety follow-up period) will be excluded from statistical analysis.

Statistical treatment comparisons will only be performed between tirzepatide 10 mg or 15 mg, and placebo. Since the trial is not adequately powered to detect difference among tirzepatide doses, comparisons among tirzepatide doses will not be performed unless otherwise specified.

Statistical summaries and results of statistical analyses will be displayed in the following order: Placebo, tirzepatide 10 mg, tirzepatide 15 mg, and pooled tirzepatide (all doses combined, if necessary).

Not all analyses described in this SAP will necessarily be included in the Clinical Study Reports (CSRs). Any analysis described in this SAP and not provided in the CSR would be available upon request. Not all displays will necessarily be created as a "static" display. Some may be incorporated into interactive display tools instead of or in addition to a static display.

<sup>a Immunogenicity related analysis is specified in Section 4.5.5.5.

